It has been proposed that aspirin could safely be stopped in ticagrelor-treated patients with a history of percutaneous coronary intervention (PCI), however this approach was not superior in a recent large randomised clinical trial [31], although another large study is ongoing [32]. Although ticagrelor monotherapy may indeed be sufficient to prevent stent thrombosis, there are likely to remain significant numbers of patients at high-risk of ongoing native plaque rupture events in whom DAPT is needed to optimise protection against future MACE, since aspirin and ticagrelor have additive antithrombotic effects [33, 34]. Aspirin, in the setting of DAPT, may therefore provide advantages of augmenting the antithrombotic effect of P2Y₁₂ inhibition but may hypothetically result in disadvantageous effects upon progression of atherothrombosis. If this profile could be optimised, then outcomes may be improved. It is also plausible that imbalance in these factors might contribute to the lack of benefit of ticagrelor over clopidogrel in patients treated with higher doses of aspirin in the PLATO study [35], although this remains to be fully explored.

We completed a pilot study of patients with a history of ACS receiving aspirin and ticagrelor, and have shown that a novel regimen of very-low-dose twice-daily aspirin (Aspirin lysine) (20 mg BD), when compared to the standard regimen of 75 mg OD, may lead to lower circulating levels of IL-6 and leukocyte count. We also observed that, compared to standard dosing, the novel regimen had reduced peak antithrombotic effect but maintained a similar trough effect, and this was associated with an improvement in haemostasis when assessed by bleeding time, which is a useful measure for assessing the impact of antithrombotic

drug combinations (in contrast to limited sensitivity for effects of antithrombotic monotherapy). There was also a trend towards increased levels of prostacyclin metabolite, suggesting reduced COX2 inhibition [36].

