Period 1: Day 1 - Day 10 (to 14)

- Participants will receive one of the following antiplatelet medication regimens for 10 to 14 days:
 - No IMP
 - No aspirin but a loading dose of ticagrelor (180 mg) taken on the last day of the medication period, 1 hour prior to endotoxin injection
 - Aspirin (aspirin lysine) 20 mg BD (only)
 - Aspirin (aspirin lysine) 20 mg BD, and a loading dose of ticagrelor (180 mg) taken on the last day of the medication period, 1 hour prior to endotoxin injection
 - Aspirin (aspirin lysine) 75 mg OD (only)

- Aspirin (aspirin lysine) 75 mg OD, and a loading dose of ticagrelor (180 mg) taken on the last day of the medication period, 1 hour prior to endotoxin injection
- Aspirin (aspirin lysine) 300 mg OD (only)
- Aspirin (aspirin lysine) 300 mg OD, and a loading dose of ticagrelor (180 mg) taken on the last day of the medication period, 1 hour prior to endotoxin injection

Visit 3 - Period 1: Day 11 (to 15)

On arrival

- Vital signs
- Physical examination
- Adverse event recording
- Concomitant medication recorded
- IMP compliance check for period 1
- Medically-qualified member of the research team to confirm that the withdrawal criteria (section 7.10) are not met, prior to proceeding further with visit

-1 hour (1 hour before endotoxin injection)

- IV cannula insertion (x2, one in each arm)
- 35.5 ml venous blood sample for baseline lab safety (full blood count, urea & electrolytes [sodium, potassium, urea and creatinine], liver function tests, clotting screen), cytokines, prostanoids, inflammatory markers and platelet function
- Bleeding time measurement
- Urine sample for prostanoid assessment at baseline
- Receive last dose of aspirin of period 1, or last dose of aspirin plus a loading dose of ticagrelor (180 mg), or no IMP, as directed by randomisation allocation
- Collect unused study medication and perform drug accountability check (sachet/pill count)
- Infusion of 250 ml 0.9% saline over 30 minutes
- 23 ml venous blood at 60 minutes after last dose of oral antiplatelet medication or equivalent time if not receiving IMP during period 1 (just before endotoxin administration)

0 hour (time of endotoxin injection)

- Continuous cardiac monitoring starts
- *E.coli* endotoxin 2 ng/kg intravenously administered over 1 minute
- Vital signs at 5, 15 and 30 minutes post-endotoxin
- Continuous IV infusion of 250 ml 0.9% saline over 1 hour
- 14 ml venous blood sample at 30 minutes post endotoxin

1 hour post endotoxin injection

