8. Circulating leukocyte count over time following endotoxin administration (measured at 0, 0.5, 1, 1.5, 2, 3, 4 and 6 hours post-endotoxin) assessed between aspirin groups (control vs. 20 mg BD vs. 75 mg OD vs. 300 mg OD, without ticagrelor) by two-way mixed ANOVA with treatment as a between-subjects factor and timepoint as a within-subjects factor.

9. AUC of the graph of bleeding time following endotoxin administration (measured at 0 and 6 hours post-endotoxin) assessed between aspirin groups (control vs. 20 mg BD vs. 75 mg OD vs. 300 mg OD, without ticagrelor) by one-way ANOVA.
10. AUC of the graphs of platelet aggregation to arachidonic acid (0.3 and 1 mmol/L), collagen (4 and 16 µg/ml) and ADP (20 µmol/L) over time following endotoxin administration (measured at 0 and 6 hours post-endotoxin) assessed between aspirin groups (control vs. 20 mg BD vs. 75 mg OD vs. 300 mg OD, without ticagrelor) by one-way ANOVA.

Between DAPT regimens:

11. Plasma TNF- α at 2 hours following endotoxin administration assessed between aspirin groups (control vs. 20 mg BD vs. 75 mg OD vs. 300 mg OD, given in combination with ticagrelor) by one-way ANOVA with treatment as a factor.
12. Plasma TNF- α over time following endotoxin administration (measured at 0, 0.5, 1, 1.5, 2, 3, 4 and 6 hours post-endotoxin) assessed between aspirin groups (control vs. 20 mg BD vs. 75 mg OD vs. 300 mg OD, given in combination with ticagrelor) by two-way mixed ANOVA with treatment as a between-subjects factor and timepoint as a within-subjects factor.
13. Plasma IL-6 at 2 hours following endotoxin administration assessed between aspirin groups (control vs. 20 mg BD vs. 75 mg OD vs. 300 mg OD, given in combination with ticagrelor) by one-way ANOVA with treatment as a factor.
14. Plasma IL-6 over time following endotoxin administration (measured at 0, 0.5, 1, 1.5, 2, 3, 4 and 6 hours post-endotoxin) assessed between aspirin groups (control vs. 20 mg BD vs. 75 mg OD vs. 300 mg OD, given in combination with ticagrelor) by two-way mixed ANOVA with treatment as a between-subjects factor and timepoint as a within-subjects factor.
15. Change in serum CRP over time following endotoxin administration (measured at 0 and 6 hours post-endotoxin) assessed between aspirin groups (control vs. 20 mg BD vs. 75 mg OD vs. 300 mg OD, given in combination with ticagrelor) by one-way ANOVA.

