16. Serum TXB₂ over time following endotoxin administration (measured at 0, 0.5, 1, 1.5, 2, 3, 4 and 6 hours post-endotoxin) assessed between aspirin groups (control vs. 20 mg BD vs. 75 mg OD vs. 300 mg OD, given in combination with ticagrelor) by two-way mixed ANOVA with treatment as a between-subjects factor and timepoint as a within-subjects factor.
17. Urinary PGI-M (measured at 0, 2, 4 and 6 hours, each adjusted for [divided by] urinary creatinine) over time following endotoxin administration assessed between aspirin groups (control vs. 20 mg BD vs. 75 mg OD vs. 300 mg OD, given in combination with ticagrelor) by two-way mixed ANOVA with treatment as a between-subjects factor and timepoint as a within-subjects factor.
18. Serum PGE₂ over time following endotoxin administration (measured at 0, 0.5, 1, 1.5, 2, 3, 4 and 6 hours post-endotoxin) assessed between aspirin groups (control vs. 20 mg BD vs. 75 mg OD vs. 300 mg OD, given in combination with ticagrelor) by two-way mixed ANOVA with treatment as a between-subjects factor and timepoint as a within-subjects factor.
19. Circulating leukocyte count over time following endotoxin administration (measured at 0, 0.5, 1, 1.5, 2, 3, 4 and 6 hours post-endotoxin) assessed between aspirin groups (control vs. 20 mg BD vs.

75 mg OD vs. 300 mg OD, given in combination with ticagrelor) by two-way mixed ANOVA with treatment as a between-subjects factor and timepoint as a within-subjects factor.

20. AUC of the graph of bleeding time following endotoxin administration (measured at 0 and 3 hours post-endotoxin) assessed between aspirin groups (control vs. 20 mg BD vs. 75 mg OD vs. 300 mg OD, given in combination with ticagrelor) by one-way mixed ANOVA.
21. AUC of the graphs of platelet aggregation to arachidonic acid (0.3 and 1 mmol/L), collagen (4 and 16 µg/ml) and ADP (20 µmol/L) over time following endotoxin administration (measured at 0 and 3 hours post-endotoxin) assessed between aspirin groups (control vs. 20 mg BD vs. 75 mg OD vs. 300 mg OD, given in combination with ticagrelor) by one-way ANOVA.

To compare aspirin monotherapy with aspirin and ticagrelor in combination:

1. Plasma TNF- α at 2 hours following endotoxin administration) compared between each aspirin regimen (control, 20 mg BD, 75 mg OD, 300 mg OD, each without ticagrelor) and each corresponding DAPT regimen (control, 20 mg BD, 75 mg OD, 300 mg OD, each with ticagrelor 90 mg BD) by paired t-tests.

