2. AUC of the graph of plasma TNF- α over time following endotoxin administration (measured at 0, 0.5, 1, 1.5, 2, 3, 4 and 6 hours post-endotoxin) compared between each aspirin regimen (control, 20 mg BD, 75 mg OD, 300 mg OD, each without ticagrelor) and each corresponding DAPT regimen (control, 20 mg BD, 75 mg OD, 300 mg OD, each with ticagrelor 90 mg BD) by paired t-tests.
3. Plasma IL-6 at 2 hours following endotoxin administration, compared between each aspirin regimen (control, 20 mg BD, 75 mg OD, 300 mg OD, each without ticagrelor) and each corresponding DAPT regimen (control, 20 mg BD, 75 mg OD, 300 mg OD, each with ticagrelor 90 mg BD) by paired t-tests.
4. AUC of the graph of plasma IL-6 over time following endotoxin administration (measured at 0, 0.5, 1, 1.5, 2, 3, 4 and 6 hours post-endotoxin) compared between each aspirin regimen (control, 20 mg BD, 75 mg OD, 300 mg OD, each without ticagrelor) and each corresponding DAPT regimen (control, 20 mg BD, 75 mg OD, 300 mg OD, each with ticagrelor 90 mg BD) by paired t-tests.
5. Change in serum CRP over time following endotoxin administration (measured at 0 and 6 hours post-endotoxin) compared between each aspirin regimen (control, 20 mg BD, 75 mg OD, 300 mg OD, each without ticagrelor) and each corresponding DAPT regimen (control, 20 mg BD, 75 mg OD, 300 mg OD, each with ticagrelor 90 mg BD) by paired t-tests.
6. AUC of the graph of serum TXB₂ over time following endotoxin administration (measured at 0, 0.5, 1, 1.5, 2, 3, 4 and 6 hours post-endotoxin) compared between each aspirin regimen (control, 20 mg BD, 75 mg OD, 300 mg OD, each without ticagrelor) and each corresponding DAPT regimen (control, 20 mg BD, 75 mg OD, 300 mg OD, each with ticagrelor 90 mg BD) by paired t-tests.
7. AUC of the graph of urinary PGI-M (measured at 0, 2, 4 and 6 hours, each adjusted for [divided by] urinary creatinine) over time following endotoxin administration compared between each aspirin regimen (control, 20 mg BD, 75 mg OD, 300 mg OD, each without ticagrelor) and each corresponding DAPT regimen (control, 20 mg BD, 75 mg OD, 300 mg OD, each with ticagrelor 90 mg BD) by paired t-tests.
8. AUC of the graph of serum PGE₂ over time following endotoxin administration (measured at 0, 0.5, 1, 1.5, 2, 3, 4 and 6 hours post-endotoxin) compared between each aspirin regimen (control, 20 mg

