BD, 75 mg OD, 300 mg OD, each without ticagrelor) and each corresponding DAPT regimen (control, 20 mg BD, 75 mg OD, 300 mg OD, each with ticagrelor 90 mg BD) by paired t-tests.

9. AUC of the graph of circulating leukocyte count over time following endotoxin administration (measured at 0, 0.5, 1, 1.5, 2, 3, 4 and 6 hours post-endotoxin) compared between each aspirin regimen (control, 20 mg BD, 75 mg OD, 300 mg OD, each without ticagrelor) and each corresponding DAPT regimen (control, 20 mg BD, 75 mg OD, 300 mg OD, each with ticagrelor 90 mg BD) by paired t-tests.
10. AUC of the graph of bleeding time following endotoxin administration (measured at 0 and 3 hours post-endotoxin) compared between each aspirin regimen (control, 20 mg BD, 75 mg OD, 300 mg OD, each without ticagrelor) and each corresponding DAPT regimen (control, 20 mg BD, 75 mg OD, 300 mg OD, each with ticagrelor 90 mg BD) by paired t-tests.
11. AUC of the graphs of platelet aggregation to arachidonic acid (0.3 and 1 mmol/L), collagen (4 and 16 µg/ml) and ADP (20 µmol/L) over time following endotoxin administration (measured at 0 and 3 hours post-endotoxin) compared between each aspirin regimen (control, 20 mg BD, 75 mg OD, 300 mg OD, each without ticagrelor) and each corresponding DAPT regimen (control, 20 mg BD, 75 mg OD, 300 mg OD, each with ticagrelor 90 mg BD) by paired t-tests.

And to model the effects of all variables (considering parallel groups):

12. Plasma TNF-α over time following endotoxin administration (measured at 0, 0.5, 1, 1.5, 2, 3, 4 and 6 hours post-endotoxin) compared between each aspirin regimen (control, 20 mg BD, 75 mg OD, 300 mg OD, each without ticagrelor) and each corresponding DAPT regimen (control, 20 mg BD, 75 mg OD, 300 mg OD, each with ticagrelor 90 mg BD) with a mixed three-way ANOVA with aspirin-dose and presence or absence of ticagrelor as between-subjects factors and timepoint as a within-subject factor.
13. Plasma IL-6 over time following endotoxin administration (measured at 0, 0.5, 1, 1.5, 2, 3, 4 and 6 hours post-endotoxin) compared between each aspirin regimen (control, 20 mg BD, 75 mg OD, 300 mg OD, each without ticagrelor) and each corresponding DAPT regimen (control, 20 mg BD, 75 mg OD, 300 mg OD, each with ticagrelor 90 mg BD) with a mixed three-way ANOVA with aspirin-dose and presence or absence of ticagrelor as between-subjects factors and timepoint as a within-subject factor.

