4. Serum TXB₂ over time following endotoxin administration (measured at 0, 0.5, 1, 1.5, 2, 3, 4 and 6 hours post-endotoxin) assessed between treatment groups (control vs. 20 mg BD vs. 75 mg OD vs. 300 mg OD, with or without ticagrelor) using a mixed effect linear model with patient as a random effect, aspirin dose, presence or absence of ticagrelor treatment and treatment period (first or second) as fixed effects, and baseline value as covariate.
5. Urinary PGI-M (measured at 0, 2, 4 and 6 hours, each adjusted for [divided by] urinary creatinine) over time following endotoxin administration, assessed between treatment groups (control vs. 20

mg BD vs. 75 mg OD vs. 300 mg OD, with or without ticagrelor) using a mixed effect linear model with patient as a random effect, aspirin dose, presence or absence of ticagrelor treatment and treatment period (first or second) as fixed effects, and baseline value as covariate.

6. Serum PGE₂ over time following endotoxin administration (measured at 0, 0.5, 1, 1.5, 2, 3, 4 and 6 hours post-endotoxin) assessed between treatment groups (control vs. 20 mg BD vs. 75 mg OD vs. 300 mg OD, with or without ticagrelor) using a mixed effect linear model with patient as a random effect, aspirin dose, presence or absence of ticagrelor treatment and treatment period (first or second) as fixed effects, and baseline value as covariate.
7. Circulating leukocyte count over time following endotoxin administration (measured at 0, 0.5, 1, 1.5, 2, 3, 4 and 6 hours post-endotoxin) assessed between treatment groups (control vs. 20 mg BD vs. 75 mg OD vs. 300 mg OD, with or without ticagrelor) using a mixed effect linear model with patient as a random effect, aspirin dose, presence or absence of ticagrelor treatment and treatment period (first or second) as fixed effects, and baseline values as covariate.
8. Bleeding time following endotoxin administration (measured at 0 and 3 hours post-endotoxin) assessed between treatment groups (control vs. 20 mg BD vs. 75 mg OD vs. 300 mg OD, with or without ticagrelor) using a mixed effect linear model with patient as a random effect, aspirin dose, presence or absence of ticagrelor treatment and treatment period (first or second) as fixed effects, and baseline values as covariate.

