APPENDIX 1 Sample collection plan

Visit	Visit description	Timepoint within visit	Safety (FBC)	Safety (Chemistry)	Safety (Clotting screen)	DNA/RNA for storage	Plasma for cytokines/storage	Serum for prostaglandins/CRP /storage	Plasma for LTA	Blood for white cell count and subsets/storage	Total for timepoint	Urine	Bleeding time
		Tube type ↳	EDTA	SST	Citrate	EDTA	Citrate	SST	Citrate	Citrate			
Whole blood to draw (ml)													
1	Enrolment		4	4	4.5						12.5		
2	Randomisation			4	4	4.5		5	9	4.5	27	✓	✓
3	Endotoxin day 1	Baseline (pre drug dose)	4	4	4.5		4.5	5	9	4.5	35.5	✓	✓
	Post drug dose/pre endotoxin						4.5	5	9	4.5	23		
	30 mins post endotoxin						4.5	5		4.5	14		
	1 hour post endotoxin						4.5	5		4.5	14	✓	
	1.5 hours post endotoxin						4.5	5		4.5	14		
	2 hours post endotoxin						9	5		9	23	✓	
	3 hours post endotoxin						4.5	5	9	4.5	23	✓	
	4 hours post endotoxin						4.5	5		4.5	14	✓	
	6 hours post endotoxin						4.5	5		4.5	14	✓	
4	(Telephone call only)										0		
5	(Telephone call only)												
6	Start of period 2		4	4	4.5						12.5		
7	Endotoxin day 2	Baseline (pre drug dose)	4	4	4.5		4.5	5	9	4.5	35.5	✓	✓
	Post drug dose/pre endotoxin						4.5	5	9	4.5	23		
	30 mins post endotoxin						4.5	5		4.5	14		
	1 hour post endotoxin						4.5	5		4.5	14	✓	
	1.5 hours post endotoxin						4.5	5		4.5	14		
	2 hours post endotoxin						9	5		9	23	✓	
	3 hours post endotoxin						4.5	5	9	4.5	23	✓	
	4 hours post endotoxin						4.5	5		4.5	14	✓	
	6 hours post endotoxin						4.5	5		4.5	14	✓	
8	(Telephone call only)										0		
9	(Telephone call only)										0		
TOTAL			16	16	18	4	99	95	63	94.5	401		

EDTA, Ethylenediaminetetraacetic acid; LTA, light transmittance aggregometry; SST, serum separator tube. See main text of protocol for other abbreviations.

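### The bleeding time analysed as 0 h is taken before the last aspirin dose and before ticagrelor, so the two-point AUC halves the 3 h ticagrelor contrast and mixes two treatment conditions

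*Protocol*

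**What the plan says.** **Schedule.** In protocol section 7.7, visits 3 and 7 each have two bleeding times. The first is in the block one hour before endotoxin. It is listed ahead of the dosing step, "Receive last dose of aspirin of period 1, or last dose of aspirin plus a loading dose of ticagrelor (180 mg), or no IMP". Appendix 1 ticks it in the row labelled "Baseline (pre drug dose") and has no tick in the next row, which is after the drug dose and before endotoxin. The second reading is at 3 h. The list of time points that closes section 7.7 calls the first reading pre-endotoxin, without saying whether it is before or after the dose.

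**Analysis.** Section 3.3 defines the endpoint as a 0 to 3 h AUC. Section 10.3.3, repeated in the SAP, has two numbered lists.
- First list, item 9 (aspirin groups without ticagrelor): "AUC of the graph of bleeding time following endotoxin administration (measured at 0 and 6 hours post-endotoxin").
- First list, item 20 (aspirin groups, all with ticagrelor): "AUC of the graph of bleeding time following endotoxin administration (measured at 0 and 3 hours post-endotoxin) assessed between aspirin groups".
- Second list, item 10 (each regimen without and with ticagrelor, paired t-tests): "AUC of the graph of bleeding time following endotoxin administration (measured at 0 and 3 hours post-endotoxin) compared between each aspirin regimen".
- Second list, item 19: a three-way ANOVA on the 0 and 3 h values, with time point as a within-subject factor.

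Section 10.6, item 8, for premature termination, plans "Bleeding time following endotoxin administration (measured at 0 and 3 hours post-endotoxin) assessed between treatment groups". It is a mixed model with a baseline covariate and no time term.

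**Rationale.** Section 2 calls bleeding time useful for drug combinations, "in contrast to limited sensitivity for effects of antithrombotic monotherapy".

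**The concern.** The analysis treats the first reading as the start of the response on study treatment. On a ticagrelor day the schedule makes it a reading before ticagrelor. On an aspirin regimen it is an end-of-interval reading on aspirin alone, and in the control group it is a reading on no drug. No bleeding time falls between the ticagrelor dose and 3 h after endotoxin.

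Bleeding time is the only test listed under haemostasis, and haemostasis under dual therapy is part of the case for the 20 mg BD regimen. A ticagrelor effect on it would be reported in diluted form and tested with less power. A comparison described as between dual-therapy regimens would rest half on readings taken without ticagrelor.

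**Working it through.** The documents give no effect size, SD or power for bleeding time, so there is no stated figure to reproduce.

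**Inputs.** Reading times: section 7.7 and Appendix 1. Ticagrelor: a single dose 1 h before endotoxin, in one period only (section 7.3). Washout: at least 5 weeks (sections 4 and 7.7), so both pre-dose readings are taken as ticagrelor-free. Pairs per regimen: 18 planned, at least 16 expected (section 10.1).

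**1. Weights.** The two-point trapezoid is AUC = (T/2) × (first + 3 h). Each reading has weight 1/2, whether T is the nominal 3 h or the actual 4 h from the -1 h block.

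**2. Item 10 against the 3 h effect.** Let D0 and D3 be the ticagrelor effects at the two readings. The time-averaged contrast is (D0 + D3)/2. A pre-dose first reading has D0 = 0, so the result is D3/2. In a simulation with a 3 h effect of 4.00, the AUC contrast was 2.00.

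**3. Item 10 against a true 0-3 h AUC effect.** Let f be the effect at 0 h (1 h after dosing) divided by the effect at 3 h, with f between 0 and 1 and the effect linear in between. The planned contrast divided by the true one is [3 × (0 + 1)/2] / [3 × (f + 1)/2] = 1/(1 + f).

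| f | Share recovered |
|---|---|
| 0 | 100% |
| 0.25 | 80% |
| 0.5 | 67% |
| 0.75 | 57% |
| 1 | 50% |

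**4. Power for item 10 (illustrative).** Assume equal SDs (set to 1), correlation rs between readings at the same visit and rb between visits. The SD of the paired difference is √(2(1 − rb)) for the 3 h value and √(2((1 + rs)/2 − rb)) for the mean of the two readings, while the effect is halved. With 16 pairs and two-sided 0.05, 80% power at 3 h needs a standardised effect of 0.749 (noncentral t).

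| rs, rb (assumed) | Effect multiplied by | Standardised effect on AUC | Power |
|---|---|---|---|
| 0.5, 0.5 | 0.707 | 0.530 | 51% |
| 0.7, 0.5 | 0.598 | 0.448 | 39% |
| 0.8, 0.5 | 0.559 | 0.419 | 35% |

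With 18 pairs, and again 80% power at 3 h, the percentages are the same.

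**5. Item 19.** In a simulation with a true 3 h effect of 4, the ticagrelor main effect averaged over both times was 2.02. The ticagrelor-by-time interaction was 4.08.

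**6. Section 10.6, item 8.** In the same simulated data, with both readings as outcomes and the visit 2 value as covariate, the ticagrelor effect was 2.02. With the 3 h value as outcome and the same-day pre-dose value as covariate, it was 4.08. The text allows either: a note in section 7.7 ties baseline to visit 2, while Appendix 1 uses the word for the same-day pre-dose row.

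**7. Item 20.** Every 3 h reading here is with ticagrelor and every first reading is without it. Let g be the aspirin-dose difference before dosing divided by that at 3 h. The standardised effect of the AUC relative to the 3 h value is ((1 + g)/2) / √((1 + rs)/2). It exceeds 1 when g is above 0.84 (rs = 0.7) or 0.73 (rs = 0.5). The documents do not give g.

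**8. Item 9.** Section 7.7 and Appendix 1 schedule no bleeding time at 6 h.

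**The case against.** **The order of entries within a block need not be the order in time, and the summary list says pre-endotoxin.** For other assays that list separates a sample before the last dose from one before endotoxin, so its label could suggest a post-dose bleeding time. But it uses the same label for urine, which Appendix 1 also places in the pre-dose row, and Appendix 1 leaves bleeding time out of the post-dose row. The pre-dose reading of the schedule stands.

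**A reader might infer that the trial reports half of the true ticagrelor effect.** The documents do not support that. Half is exact against the 3 h effect, but section 3.3 defines a 0-3 h AUC. Against that, half is the low end of the range in step 3.

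**A reader might infer that dose comparisons under ticagrelor must lose power.** Step 7 shows that they may lose or gain. What stands is that item 20 mixes two conditions.

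**The pre-dose reading has value.** It follows 10 to 14 days of dosing on the aspirin regimens, and section 2 treats peak and trough effects as distinct. That is a reason to report it separately, not to average it into a ticagrelor contrast.

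**Not every analysis is affected alike.** Item 9 has no ticagrelor arm, so the dilution does not arise there. Item 19 keeps an interaction that could show the effect. Section 10.6, item 8, is ambiguous rather than shown to be wrong. Urinary PGI-M also starts from a pre-dose sample, and a reader might extend the point to it. That value carries only 1/6 of the 0-2-4-6 h AUC, and no resulting error is shown.

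**Conclusion.** The point holds in a limited form. The 0 h label contradicts the schedule, and the two-point AUC in item 10 gives half its weight to a reading that ticagrelor cannot have affected. The time-averaged contrast is exactly half of the 3 h effect. It is 50% to 100% of a true 0-3 h AUC effect if the effect at 1 h after dosing lies between nil and the 3 h effect. The fall in power to about 35% to 51% rests on assumed correlations and applies only to the paired contrast.

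Item 20 does not cleanly compare dual-therapy regimens, and the direction and size of any power change there are not established. The item 19 main effect is halved. Section 10.6, item 8, halves the effect under one reading of baseline and not under the other. Item 9 relies on a reading that is never scheduled. Bleeding time is a secondary endpoint, and the primary TNF-α analysis is unaffected.

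**What to change.** - **Endpoint.** Define bleeding time as the 3 h value in protocol section 3.3, section 10 and the SAP.
- **Ticagrelor contrast (item 10).** Analyse the within-person difference in 3 h values, with the difference in same-day pre-dose values as covariate.
- **Aspirin-regimen contrasts (items 9 and 20).** Analyse the 3 h value with the visit 2 pre-medication value as covariate, because the same-day pre-dose value already carries the aspirin effect. This replaces the 6 h reading in item 9.
- **Item 19.** Use the 3 h value as the outcome, in line with the new endpoint.
- **Section 10.6, item 8.** State the outcome time and which reading is the baseline.
- **Pre-dose reading.** Report it separately, as an end-of-interval measure before ticagrelor.
- **Labels.** Reconcile the pre-endotoxin and 0 h labels with section 7.7 and Appendix 1.

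The cost is small: one secondary endpoint definition and the matching analysis wording change in both documents. Every reading needed is already scheduled.
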